## 1 PROTOCOL SUMMARY

### 1.1 Synopsis

**Protocol Title:** A Phase 3 randomized, active-comparator-controlled clinical study to evaluate the efficacy and safety of Ezetimibe/Atorvastatin combination tablet (MK-0653C) as second line lipid lowing treatment in Chinese participants

**Short Title:** MK-0653C vs. atorvastatin in Chinese hypercholesterolemic participants

**Acronym:** MK0653C-439

### Hypotheses, Objectives, and Endpoints:

All objectives and hypotheses will be evaluated in Chinese participants with hypercholesterolemia, inadequately controlled with 10 mg or 20 mg atorvastatin monotherapy.

Objectives	Endpoints
Primary	

Objective: To evaluate the percent change in LDL-C from baseline to Week 12 of MK-0653C 10/10 mg compared to atorvastatin 20 mg (Cohort A). Hypothesis: MK-0653C 10/10 mg is superior to atorvastatin 20 mg (Cohort A) in percent change from baseline in LDL-C to 12 weeks after treatment.

Objective: To evaluate the percent change in LDL-C from baseline to Week 12 of MK-0653C 10/20 mg compared to atorvastatin 40 mg (Cohort B). Hypothesis: MK-0653C 10/20 mg is superior to atorvastatin 40 mg (Cohort B) in percent change from baseline in LDL-C to 12 weeks after treatment.

 
Overall success is determined by a success on at least one hypothesis.
	

Low-Density Lipoprotein – Cholesterol (LDL-C) level

Objectives	Endpoints
Secondary	

Objective: To evaluate the safety and tolerability of administrated MK-0653C 10/10 mg and MK-0653C 10/20 mg once daily dosing through 12 weeks.

	

Adverse events

Laboratory parameters and vital signs

Study drug discontinuation

### Overall Design:

Study Phase	Phase 3
Primary Purpose	Treatment
Indication	Hypercholesterolemia
Population	Chinese participants with hypercholesterolemia inadequately controlled by 10 mg or 20 mg atorvastatin.
Study Type	Interventional
Intervention Model	Parallel This is a multi-site study.
Type of Control	Active Control Without Placebo
Study Blinding	Double-blind with in-house blinding
Masking	Participant or Subject Investigator Monitor
Estimated Duration of Study	The Sponsor estimates that the study will require approximately 1.5 years from the time the first participant signs the informed consent until the last participant's last study-related telephone call or visit.

**Number of Participants:**

Approximately 450 participants will be randomized across two cohorts defined by statin dose at the screening visit. In Cohort A (atorvastatin  $\leq$ 10 mg or equivalent), 180 participants will be randomized, and in Cohort B (atorvastatin 20 mg or equivalent), 270 participants will be randomized.

**Intervention Groups and Duration:**

Intervention Groups	During double-blinded treatment period:						
	Intervention Group Name	Drug	Dose Strength	Dose Frequency	Route of Admin.	Regimen/ Treatment Period	Use
A1	MK-0653C FDC (ezetimibe 10 mg + atorvastatin 10 mg)	10 mg/ 10 mg	QD	Oral	Randomization treatment: 12 weeks	Study treatment	
	Placebo atorvastatin	0 mg	QD	Oral	Randomization treatment: 12 weeks	Dummy with study treatment	
A2	atorvastatin	20 mg	QD	Oral	Randomization treatment: 12 weeks	Active control	
	Placebo of MK-0653C FDC (ezetimibe 10 mg + atorvastatin 10 mg)	0 mg	QD	Oral	Randomization treatment: 12 weeks	Dummy with active control	
B1	MK-0653C FDC (ezetimibe 10 mg + atorvastatin 20 mg)	10 mg/ 20 mg	QD	Oral	Randomization treatment: 12 weeks	Study treatment	
	Placebo of atorvastatin	0 mg	QD	Oral	Randomization treatment: 12 weeks	Dummy with study treatment	
B2	atorvastatin	20 mg x 2	QD	Oral	Randomization treatment: 12 weeks	Active control	
	Placebo of MK-0653C FDC (ezetimibe 10 mg+ atorvastatin 20 mg)	0 mg	QD	Oral	Randomization treatment: 12 weeks	Dummy with active control	

Total Number	4
Duration of Participation	Each participant will participate in the study for approximately 21 weeks, from the time the participant signs the Informed Consent Form (ICF) through the final contact. After a screening phase of 2 weeks followed by an atorvastatin treatment period of approximately 5 weeks, each participant who has not met treatment target criteria will receive assigned intervention for approximately 12 weeks. After the end of treatment each participant will be followed for 14 days.

**Study Governance Committees:**

Steering Committee	No
Executive Oversight Committee	No
Data Monitoring Committee	No
Clinical Adjudication Committee	No
Study governance considerations are outlined in Appendix 1.	

**Study Accepts Healthy Volunteers:** No

A list of abbreviations used in this document can be found in Appendix 8.

## 1.2 Schema

The study design is depicted in [Figure 1](#).

[figure not shown]

Figure 1 Study Design

### 1.3 Schedule of Activities (SoA)

Study Period	Screening	Active run-in period (5 weeks)		Treatment (12 weeks)			Follow-up (14 days post last dose)	Notes
Visit Number/Title	Visit 1/ Screening	Visit 2	Visit 3	Visit 4/ baseline	Visit 5	Visit 6/ Discontinuation	Phone call	
Scheduled Hour, Day, Week, etc., and Window:	Week -7/-6	Week -5 (±7 days)	Week -1 (+3 days)	Week 0 (±3 days)	Week 6 (±7 days)	Week 12 (±7 days)	±3 days	The dates of Visit 3 and Visit 4 will be decided based on the date of Visit 2, while the dates of Visit 5 & Visit 6 will be decided based on the date of Visit 4.
Administrative Procedures								
Informed Consent	X							
Inclusion/Exclusion Criteria	X			X				
Participant Identification Card	X							The card will be updated once randomized.
Medical History	X							
Prior/Concomitant Medication Review	X	X	X	X	X	X		
Assignment of Screening Number	X							
LDL-C treatment target evaluation based on Cardiac Risk assessment	X							Based on Chinese Guidelines on Prevention and Treatment of Dyslipidemia in Adults (2016 Edition).
Monitor Dietary/Exercise Compliance	X	X	X	X	X	X		
Monitor Medication Compliance			X	X	X	X		
Assignment of Treatment/Randomization number				X				

Study Period	Screening	Active run-in period (5 weeks)		Treatment (12 weeks)			Follow-up (14 days post last dose)	Notes
Visit Number/Title	Visit 1/ Screening	Visit 2	Visit 3	Visit 4/ baseline	Visit 5	Visit 6/ Discontinuation	Phone call	
Scheduled Hour, Day, Week, etc., and Window:	Week -7/-6	Week -5 (±7 days)	Week -1 (+3 days)	Week 0 (±3 days)	Week 6 (±7 days)	Week 12 (±7 days)	±3 days	The dates of Visit 3 and Visit 4 will be decided based on the date of Visit 2, while the dates of Visit 5 & Visit 6 will be decided based on the date of Visit 4.
Run-in atorvastatin administration/dispensing		X						
MK-0653C/ Atorvastatin + matching placebo administration/dispensing				X	X			
Efficacy Procedures								
Lipid Panel A	X		X	X	X	X		LDL-C, total cholesterol (TC), HDL-C, non-HDL-C, and Triglyceride (TG). Blood sample should be drawn after at least 10-hour fasting. Otherwise the visit need to be rescheduled. Result of local lab within 4 weeks prior to Visit 1 can be used as reference for participant screening.
Apo protein (Apo) B				X	X	X		Blood sample should be drawn after at least 10-hour fasting. Otherwise the visit needs to be rescheduled.
Safety Procedures								
Full Physical Examination including height and weight	X			X		X		

Study Period	Screening	Active run-in period (5 weeks)		Treatment (12 weeks)			Follow-up (14 days post last dose)	Notes
Visit Number/Title	Visit 1/ Screening	Visit 2	Visit 3	Visit 4/ baseline	Visit 5	Visit 6/ Discontinuation	Phone call	
Scheduled Hour, Day, Week, etc., and Window:	Week -7/-6	Week -5 (±7 days)	Week -1 (+3 days)	Week 0 (±3 days)	Week 6 (±7 days)	Week 12 (±7 days)	±3 days	The dates of Visit 3 and Visit 4 will be decided based on the date of Visit 2, while the dates of Visit 5 & Visit 6 will be decided based on the date of Visit 4.
Vital Signs (heart rate, blood pressure)	X	X	X	X	X	X		
12-lead ECG	X							ECG will performed locally and results should be checked and confirmed by the investigator or qualified designee.
Urine/ Serum β-Human Chorionic Gonadotropin (β-hCG; WOCBP only)	X			X	X	X		Serum β-hCG test is determined by central lab if urine pregnancy performed at the site is positive.
fT4 and TSH	X							Result of local lab within 4 weeks prior to Visit 1 can be used as reference for participant screening.
Hematology	X			X		X		Result of local lab within 4 weeks prior to Visit 1 can be used as reference for participant screening.
Urinalysis	X			X		X		Result of local lab within 4 weeks prior to Visit 1 can be used as reference for participant screening.

Study Period	Screening	Active run-in period (5 weeks)		Treatment (12 weeks)			Follow-up (14 days post last dose)	Notes
Visit Number/Title	Visit 1/ Screening	Visit 2	Visit 3	Visit 4/ baseline	Visit 5	Visit 6/ Discontinuation	Phone call	
Scheduled Hour, Day, Week, etc., and Window:	Week -7/-6	Week -5 (±7 days)	Week -1 (+3 days)	Week 0 (±3 days)	Week 6 (±7 days)	Week 12 (±7 days)	±3 days	The dates of Visit 3 and Visit 4 will be decided based on the date of Visit 2, while the dates of Visit 5 & Visit 6 will be decided based on the date of Visit 4.
Chemistry	X		X	X	X	X		Blood sample should be drawn after at least 10-hour fasting. Otherwise the visit need to be rescheduled. Result of local lab within 4 weeks prior to Visit 1 can be used as reference for participant screening.
AE/SAE Monitoring	X	X-----X						The serious adverse events occurred within 14 days after last study drug administration must be reported to Sponsor.

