Participants who meet all eligibility criteria will be enrolled in a 5-week active run-in period after they discontinue the current statins with appropriate wash-out interval. Current statin is used to determine the allocation of different cohort: the participants who are currently treated at stable daily dose of 10 mg atorvastatin or other statin equivalent to or less than atorvastatin 10 mg will be assigned to Cohort A and will receive 10 mg atorvastatin during the run-in period; and the participants who are currently treated by atorvastatin at stable 20 mg or other statins equivalent to atorvastatin 20 mg will be assigned to cohort B and will receive 20 mg

atorvastatin during the run-in phase. The dose of other statins equivalent to atorvastatin can be found in [Table 3](#).

After the run-in period, the participants within either cohort who have not met their treatment goals for LDL-C according to their risk levels will be randomized into 2 cohorts to receive either MK-0653C or atorvastatin monotherapy (at twice the atorvastatin dose contained in MK-0653C) during a 12 weeks double-blind treatment period:

- Cohort A: Participants will be randomized to receive either MK-0653C 10/10 mg (containing ezetimibe 10 mg + atorvastatin 10 mg) or atorvastatin 20 mg in a 1:1 ratio;
- Cohort B: Participants will be randomized to receive either MK-0653C 10/20 mg (containing ezetimibe 10 mg + atorvastatin 20 mg) or atorvastatin 40 mg in a 1:1 ratio.

Participants who completed the trial or administered at least one dose of study intervention but prematurely discontinued will be followed by phone call 14 days after the last dose to assess serious adverse events (SAEs) and information will be documented on the follow-up visit page.

Specific procedures to be performed during the study, as well as their prescribed times and associated visit windows, are outlined in the SoA in Section 1.3. Details of each procedure are provided in Section 8.

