#### **8.4.1 Time Period and Frequency for Collecting AE, SAE, and Other Reportable Safety Event Information**

All AEs, SAEs, and other reportable safety events that occur after the consent form is signed but before intervention allocation/randomization must be reported by the investigator if the participant is receiving placebo run-in or other run-in treatment, if the event causes the participant to be excluded from the study, or is the result of a protocol-specified intervention, including but not limited to washout or discontinuation of usual therapy, diet, or a procedure.

From the time of intervention allocation/randomization through 14 days following cessation of treatment, all AEs, SAEs, and other reportable safety events must be reported by the investigator.

Additionally, any SAE brought to the attention of an investigator at any time outside of the time period specified in the previous paragraph must be reported immediately to the Sponsor if the event is considered related to study intervention.

Investigators are not obligated to actively seek AEs or SAEs or other reportable safety events in former study participants. However, if the investigator learns of any SAE, including a death, at any time after a participant has been discharged from the study, and he/she considers the event to be reasonably related to the study intervention or study participation, the investigator must promptly notify the Sponsor.

All initial and follow-up AEs, SAEs, and other reportable safety events will be recorded and reported to the Sponsor or designee within the time frames as indicated in [Table 5](#).

Table 5 Reporting Time Periods and Time Frames for Adverse Events and Other Reportable Safety Events

Type of Event	Reporting Time Period: Consent to Randomization/ Allocation	Reporting Time Period: Randomization/ Allocation through Protocol-specified Follow-up Period	Reporting Time Period: After the Protocol-specified Follow-up Period	Time Frame to Report Event and Follow-up Information to Sponsor:
Nonserious Adverse Event (NSAE)	Report if: - due to protocol-specified intervention - causes exclusion - participant is receiving placebo run-in or other run-in treatment	Report all	Not required	Per data entry guidelines

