### **8.11.5 Poststudy (follow-up visit)**

Participants will be followed-up by phone approximately 14 days after the last dose of study intervention to determine if any AEs have occurred since the last clinic visit.

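### For participants who complete treatment, the last safety call may be made up to 3 days before the 14-day adverse-event reporting period ends

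*Combined protocol and SAP*

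**What the plan says.** **Timing of the call.** The last column of the Schedule of Activities (Section 1.3) is headed "Follow-up (14 days post last dose". It holds a single phone call, and the window row gives ±3 days.

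**Period to be covered.** Three places set it at 14 days:
- Section 8.4.1: "through 14 days following cessation of treatment, all AEs, SAEs, and other reportable safety events must be reported by the investigator".
- The note to the AE/SAE monitoring row in Section 1.3, for serious events: "The serious adverse events occurred within 14 days after last study drug administration must be reported to Sponsor".
- The synopsis, under intervention groups and duration: "After the end of treatment each participant will be followed for 14 days".

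**Purpose of the call.** Section 4.1 says participants "will be followed by phone call 14 days after the last dose to assess serious adverse events (SAEs"). Section 8.11.5 is looser on timing and wider on content: "Participants will be followed-up by phone approximately 14 days after the last dose of study intervention to determine if any AEs have occurred". The look-back there starts at the preceding clinic visit.

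**After the call.** For a participant who completes treatment, Visit 6 is the last clinic visit and the call is the last scheduled contact. Section 8.4.1 adds: "Investigators are not obligated to actively seek AEs or SAEs or other reportable safety events in former study participants".

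**The concern.** A call can ask only about days that have already passed. If the schedule accepts a call before Day 14, the last prompted question can come before the end of the period in which every AE and SAE must be reported. Section 8.4.1 and Table 5 keep only drug-related SAEs reportable after the follow-up period. Non-serious AEs and unrelated SAEs from the last days of the period therefore rely on this call or on the participant coming forward.

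Safety and tolerability is the trial's only secondary objective. Section 9.6.2 compares the percentages of participants with any AE and any serious AE between arms with confidence intervals, and it states no cut-off that would leave these days out. At stake is a possible small under-count of late events, and a period of active questioning whose length depends on the day the site happens to call.

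**Working it through.** The plan states no figure to reproduce, so the check is day arithmetic. Days are counted from the last dose.

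**Inputs**
- Nominal call day 14, window −3 to +3 days (Section 1.3).
- Reporting period through Day 14 (Section 8.4.1; the same length in the Section 1.3 note and the synopsis).
- 450 participants randomized and a 10% drop-out rate (Section 9.9). That rate was set for having LDL-C data at Week 12, so it is only a rough proxy for not completing treatment.
- Treatment of 12 weeks, or 84 days (synopsis).

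**1. Permitted call days.** Earliest 14 − 3 = Day 11. Latest 14 + 3 = Day 17. That makes 7 permitted days.

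**2. Days left unasked**, as max(0, 14 − call day):

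| Call day | Days unasked | Share of 14 days |
|---|---|---|
| 11 | 3 | 3/14 = 21% |
| 12 | 2 | 2/14 = 14% |
| 13 | 1 | 1/14 = 7% |
| 14 to 17 | 0 | 0% |

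**3. How many participants.** Approximate completers: 450 × (1 − 0.10) = 405. The documents give no distribution of call dates, so the number called early could be anything from 0 to 405. For illustration, with calls spread evenly over the 7 days, 3/7 = 43% are early, and 405 × 3/7 = 174.

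**4. Average loss under that same even spread.** (3 + 2 + 1 + 0 + 0 + 0 + 0)/7 = 0.86 day per completer. That is 0.86/14 = 6% of the post-treatment period, or 0.86/(84 + 14) = 0.9% of the whole reporting period from randomization. Calls clustered tightly on Day 14 would make it smaller.

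**5. With a one-sided window.** Calls fall on Days 14 to 17, and max(0, 14 − call day) = 0 throughout. Only the hours after a call made on Day 14 itself remain.

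**6. Whether other text closes the gap.** Section 8.11.5 places the call only approximately at Day 14 and has it look back to the last clinic visit, so a Day 11 call satisfies it. The end column of the AE/SAE monitoring bar in Section 1.3 could not be read in the text available, but wherever it ends it adds no contact after the call.

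**The case against.** The best case on the other side has five parts.

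- **Not everyone lacks a later contact.** A reader might infer that no participant is seen after an early call. The documents do not support that. Sections 7.1 and 8.11.4 keep participants who stop study drug early in the study, so Visit 5 or Visit 6 may follow their call and recover the missed days. This stands, and it limits the point to completers.
- **The days are not unobserved.** The duty to report through Day 14 does not depend on the call date. Participants carry a card with site telephone numbers (Section 8.1.3), known events are followed up (Section 8.4.3), and clinically significant laboratory abnormalities within 14 days of the last dose are to be retested (Section 8.3.4). It is also arguable whether the sentence on former participants applies to Days 12 to 14, since it follows text on events outside the reporting period. This stands too: what is missing is a prompted question, not the duty to report.
- **A headcount is not established.** A reader might apply 3/7 to all 450 randomized and get 193. That counts non-completers and rests on an even spread of calls that nothing in the documents supports.
- **No planned conclusion is shown to change.** A reader might infer biased safety comparisons. The window is the same in both blinded arms of each cohort, so no such bias is expected. Eleven of the twelve Tier 1 endpoints in Table 7 need ALT, AST or CK values, and scheduled chemistry ends at Visit 6. Visit 6 has its own ±7-day window, so follow-up length already varies.
- **A symmetric window is a legitimate choice.** No text requires the call on or after Day 14. That is true, but then the schedule does not deliver the 14 days of follow-up that the synopsis promises and Section 8.4.1 relies on.

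The first four points reduce the size of the concern. None removes the mismatch for completers.

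**Conclusion.** The point holds in limited form. For participants who complete treatment, a compliant call on Day 11, 12 or 13 ends active questioning 3, 2 or 1 days before the reporting period closes, and nothing scheduled afterwards makes up for it. This follows directly from the documents and needs no assumption.

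The number affected is not known. It lies between none and all completers. The figure of about 174 of 405 rests on two assumptions: evenly spread calls, and the 10% drop-out rate as a proxy for non-completion. The likely consequence is a small under-count of non-serious AEs and unrelated SAEs in the last days of the period. The documents do not support a claim of bias between arms, of any effect on LDL-C or the scheduled laboratory endpoints, or of events certain to be lost. The change is worth making because it is cheap and bears on the only secondary objective.

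**What to change.** In Section 1.3, change the window for the follow-up call from ±3 days to 0 to +3 days, so that it falls on Days 14 to 17 after the last dose. The same row already uses a one-sided window for Visit 3 (+3 days).

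In Sections 4.1 and 8.11.5, state in the same terms that the call asks about all AEs and SAEs through Day 14. At present Section 4.1 limits it to serious events, while Section 8.11.5 covers any AE.

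**Cost.** One cell and two short text edits, with no added visit, sample or treatment. A participant who would have been called on Day 11 is called 14 − 11 = 3 to 17 − 11 = 6 days later; the latest permitted day does not move. Sites have 4 permitted days instead of 7, so a few more calls may fall outside the window. The variation from the Visit 6 window remains.

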## 2 INTRODUCTION

Atherosclerosis has traditionally been regarded as a disease primarily characterized by the progressive fatty debris in the arterial wall followed by progressive stenosis, and consequently rupture of this plaque, resulting in occlusive thrombosis and eventually cause life-threatening heart attack, stroke and so on. Dyslipidemia characterized by the increase of low-density lipoprotein cholesterol (LDL-C) or TC is an important risk factor for atherosclerotic cardiovascular diseases. Over the last 30 years, the blood lipid level in the Chinese population has gradually increased, and the incidence of dyslipidemia has significantly increased [Moran, A., et al 2010], accompanied by a significant change in disease profile: coronary heart disease became the most predominant heart disease.

The reduction of LDL-C levels can significantly decrease the development and mortality risks of atherosclerotic cardiovascular diseases which were already proved by great lot of evidences since landmark 4S trial. The analytic results of the Cholesterol Treatment Trial indicate that 1 mmol/L LDL-C reduction by statin therapy in populations with different cardiovascular risk stratifications can produce a 20% the relative risk reduction of major cardiovascular events and 10% risk reduction of all-cause mortality, whereas the mortality caused by non-cardiovascular reasons does not increase. Meta-analyses and epidemiology studies have shown that the reduction in CHD risk is proportional to the absolute change in LDL-C, i.e., greater reductions of LDL-C lead to greater cardiovascular risk reductions [Stamler, J., et al 1986] [Chen, Z., et al 1991] [Szatrowski, T. P., et al 1984] [Gould, A. L., et al 1998].

Statin was proved to be a potent LDL-C lowing agent and was widely used in primary prevention and secondary prevention of CV event. However, doubling statin dose did not correspond to a doubled LDL-C reduction. Introduction of other lipid lowing agents can provide greater LDL-C reduction when added to a statin and was recommended by local guideline. Ezetimibe provides greater improvements in lipid profile and goal attainment when added to a statin compared to a statin monotherapy [Stein, E., et al 2004] [Goldberg, A. C., et al 2004] [Pearson, T. A., et al 2005] [US Prescribing Information 2013] [UK Summary of Product Characteristics 2013].

Cumulatively, there were approximately 1,038,850 patient-years of treatment with ezetimibe/atorvastatin, of which approximately 2875 subjects treated with ezetimibe/atorvastatin fixed dose combination, and approximately 3,252 subjects treated with coadministered ezetimibe (+) atorvastatin in Marketing Authorization Holder-sponsored clinical trials. Data from trials and experience of co-administration provide the largest body of efficacy and safety data for the FDCs. And 2 definitive bioequivalence studies established the comparability between the FDC and the corresponding individual ezetimibe and atorvastatin tablets when co-administered [Ballantyne, C. M., et al 2005] [Catapano, A., et al 2005].

Based on the favorable efficacy and risk profile of co-administration of atorvastatin and ezetimibe and the proved bioequivalent of FDC to co-administration of atorvastatin and ezetimibe, MK-0653C has been approved in 49 countries by the time of Feb 2018.

